According to a meta-analysis performed by Butler et al., PPIs are frequently used in patients undergoing pancreaticoduodenectomy, with 86% of surgeons prescribing them after pancreatic resection. Forty-six percent of surgeons continue their patients on these medications for life, while 25% give the prescriptions for 30 days postoperatively (18). The main indication for their use is to reduce the occurrence of postoperative marginal ulcers, a morbid complication of pancreaticoduodenectomy with a reported average incidence of 2.0% after pylorus-preserving pancreaticoduodenectomy and 2.6% after classic pancreaticoduodenectomy (18). However, the onset of marginal ulcers is often delayed, with the median time for development of marginal ulceration after pancreaticoduodenectomy being 15.5 months (18, 19).

PPIs have been effective in decreasing the incidence of postoperative marginal ulcers. The development of marginal ulcers is driven by two mechanisms:

1. Local inflammation, ischemic changes at the anastomotic site, foreign bodies (sutures, staples), which is the primary mechanism in the immediate postoperative period, and
2. The direct effect of gastric acid on jejunal mucosa which is the primary mechanism in later periods (19).

Increased gastric acid production, low gastric pH, and prolonged duration of low pH are associated with marginal ulcers (20). However, the recommendations regarding the timing and duration of their use after pancreaticoduodenectomy remain unclear and need to be defined.

In our recently completed retrospective chart review (IRB ID: 201711053), we evaluated the

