10.5.2 Analysis of the Primary Endpoint

The primary outcome is the incidence of post-operative delayed gastric emptying using the ISGPS criteria and MAGS grading, coded as yes and no. The rate per group, odds ratio (OR) and the associated 95% confidence intervals (CIs) will be calculated assuming a binomial distribution. The logistic regression model will be considered to investigate the effect of PPIs accounting for the interested variables on the incidence of post-operative delayed gastric emptying. The interested variables include age, gender, body mass index, comorbidities, preoperative proton pump inhibitor usage, and surgical reconstruction method. The relationships between these variables and the endpoint may exist.

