10.5.3 Analysis of Secondary Endpoint(s)

Secondary endpoints include the incidence of surgical complication and marginal ulcer free survival. Surgical complication is defined by the Modified Accordion Grading System, coded as yes and no. The similar statistical approach to the primary endpoint will be employed. Any clinical diagnosis is used to define a marginal ulcer within 90 days after surgery. MUFS is defined as the days from the date of randomization to diagnosis of a marginal ulcer. The patients without marginal ulcer are censored at the date of last follow-up. The Kaplan-Meier method will be used to calculate the probability of marginal ulcer free survival at specific time points, e.g. 30 days, 90 days after surgery. The 95% CIs will be also provided. Differences between groups will be determined by log-rank tests. Cox

proportional-hazards models will be used to evaluate the effect of PPIs accounting for the other interested variables.

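### The covariate-adjusted Cox model planned for 90-day marginal ulcers (10.5.3) has too few expected events to support it: about 0.6 to 4.3 ulcers in the whole trial at the cited incidence

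*Combined protocol and SAP*

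**What the plan says.** Marginal ulcer-free survival (MUFS) is a secondary endpoint. Section 10.5.3 sets the event: "Any clinical diagnosis is used to define a marginal ulcer within 90 days after surgery". Three analyses follow: Kaplan-Meier probabilities with 95% intervals at times such as 30 and 90 days; a group comparison ("Differences between groups will be determined by log-rank tests"); and Cox models, where "proportional-hazards models will be used to evaluate the effect of PPIs accounting for the other interested variables". The commitment to the Cox model is firmer than the wording in 10.5.2, which only says that a logistic model is to be considered for the primary endpoint.

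Section 10.5.3 does not list its covariates. The only list is in 10.5.2: "The interested variables include age, gender, body mass index, comorbidities, preoperative proton pump inhibitor usage, and surgical reconstruction method".

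On frequency and timing, section 1.0 gives a "reported average incidence of 2.0% after pylorus-preserving pancreaticoduodenectomy and 2.6% after classic pancreaticoduodenectomy", without a length of follow-up, and then "the median time for development of marginal ulceration after pancreaticoduodenectomy being 15.5 months". Section 5.3 ends record review at 90 days or death.

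Section 10.2 sizes the trial on delayed gastric emptying and surgical complications only. The documents state no expected number of ulcers, no power for MUFS, and no rule for sparse events.

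**The concern.** The protocol's own background describes an uncommon event that mostly appears long after the observation window closes. A multivariable Cox model needs events, not patients. If one arm has no ulcer, the partial likelihood has no finite maximum for the treatment effect, adjusted or not. An empty covariate category can cause the same failure for that covariate. With a handful of ulcers the model may converge, but its estimates would be too unstable to interpret.

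Readers will look at this comparison, because section 1.0 names ulcer prevention as the chief reason for giving PPIs after this operation and expects the trial to discourage their routine early use. If the model fails, the analyst has to choose a substitute after seeing the data. If it runs and gives a non-significant hazard ratio, that could be taken to mean that withholding PPIs leaves ulcer risk unchanged.

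**Working it through.** **The plan's own figure.** There is none for ulcers. The sample size can be checked: 240 / (1 − 0.27) = 328.8, in line with the 330 in 10.2.

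**Inputs**
- Incidence r: 2.0–2.6% (1.0).
- Median onset: 15.5 months (1.0).
- Window: 90 days, taken as 3 months (5.3, 10.5.3).
- N: 240 dosed patients (Protocol Summary) or 330 randomized (10.2, 10.3). Section 10.4.1 defines the efficacy set as all randomized, while 5.1 calls only dosed patients evaluable, so both are shown. Allocation is 1:1.
- Coefficients: treatment plus six variables, one term each = 7. Comorbidities or reconstruction method could need more.

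**Step 1. Share of ulcers by day 90 (assumption).**
- Constant hazard with that median: 1 − 2^(−3/15.5) = 0.1255, about 12.6%.
- Ceiling: 50%, because day 90 falls before the median.

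**Step 2. Expected ulcers, both arms at the cited rate: N × r × share.**

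| N | r | Constant hazard | 50% ceiling |
|---|---|---|---|
| 240 | 2.0% | 0.60 | 2.40 |
| 240 | 2.6% | 0.78 | 3.12 |
| 330 | 2.0% | 0.83 | 3.30 |
| 330 | 2.6% | 1.08 | 4.29 |

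**Step 3. Events per coefficient.** 0.60/7 = 0.09 up to 4.29/7 = 0.61.

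**Step 4. Chance that at least one arm has no ulcer.** With Poisson counts and total mean μ, this is 1 − (1 − e^(−μ/2))².
- Constant hazard: 93% (μ = 0.60) to 83% (μ = 1.08).
- 50% ceiling: 51% (μ = 2.40) to 22% (μ = 4.29).

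**Step 5. Ignore the onset time altogether.** If every cited ulcer fell within 90 days: 240 × 2.0% = 4.8 to 330 × 2.6% = 8.6 events, or 0.69 to 1.23 per coefficient.

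**Step 6. Sensitivity: a higher placebo rate.** The multiplier k = 2 to 5 is an assumption and is not in the documents. With the PPI arm at the cited rate, the totals in step 2 are multiplied by (1 + k)/2.
- Events: 0.60 × 1.5 = 0.90 up to 4.29 × 3 = 12.87.
- Per coefficient: 0.90/7 = 0.13 up to 12.87/7 = 1.84.
- Chance of an empty arm, 1 − (1 − e^(−a))(1 − e^(−ka)), where a is the PPI-arm mean:
  - Constant hazard: 88% (a = 0.30, k = 2) to 61% (a = 0.54, k = 5).
  - 50% ceiling: 36% (a = 1.20, k = 2) to 12% (a = 2.15, k = 5).

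**Step 7. What can still be reported from an empty arm.** Standard Kaplan-Meier intervals are zero-width or undefined there (10.5.3 names no interval method). The exact two-sided 95% upper limit is 1 − 0.025^(1/n): 3.0% for 0/120 and 2.2% for 0/165.

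**The case against.** - **The counts rest on assumptions.** The cited incidence has no stated follow-up. Section 1.0 describes a separate early mechanism (local inflammation, ischemia, foreign bodies), which fits poorly with a constant hazard. Counting any clinical diagnosis may also capture more ulcers than the cited rate does. This stands, and it is why the 50% ceiling and step 5 are shown. The model remains unsupported in both.
- **The cited rate may understate the placebo risk.** Section 1.0 reports "86% of surgeons prescribing them after pancreatic resection" and says that "PPIs have been effective in decreasing the incidence of postoperative marginal ulcers". A reader might infer that the placebo rate is several times higher. The documents give no size for that effect, and the survey figure describes prescribers, not the patients behind the incidence. Study drug also lasts at most 10 doses, so a large contrast over 90 days is not obvious. Step 6 is therefore only a sensitivity analysis.
- **The full covariate set is not mandated.** True: 10.5.3 leaves it undefined. A smaller model would ease the events-per-coefficient problem but not the empty-arm problem, which affects the treatment term alone.
- **The log-rank test can work.** In the most favorable corner (12.9 events, fivefold rate) its power is about 69% by a Poisson approximation and 82% by Schoenfeld's formula. It can be computed wherever ulcers occur, and 10.2 claims no power for it. A reader might infer that the whole MUFS comparison is an error. That is not supported: the defect lies in the adjusted Cox model.
- **The endpoint is secondary.** That stands, and it limits the weight of the point.

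**Conclusion.** The concern holds for the covariate-adjusted Cox model only. On the cited incidence and median, the hazard ratio would often have no finite estimate, and otherwise would rest on fewer than one event per coefficient. Even with a placebo rate five times higher and half of all ulcers by day 90, there are fewer than two events per coefficient. These results assume the cited incidence is cumulative over long follow-up, a day-90 share between the constant-hazard value and the ceiling, and all six variables entering with treatment.

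A reader might also infer that the plan intends to claim ulcer safety or non-inferiority. It makes no such claim. The risk is that a null result is over-read, since 10.5.3 gives no caution about event numbers. Delayed gastric emptying, the primary endpoint, is not touched. This is a worthwhile, inexpensive correction to a secondary analysis.

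**What to change.** In 10.5.3:
1. Remove the covariate-adjusted Cox model for MUFS.
2. Report the number of ulcers, the 90-day risk by arm and the risk difference, with exact 95% confidence intervals.
3. Keep the planned Kaplan-Meier estimates, which also handle records that end before day 90, and the log-rank test.
4. Add a sentence that, with so few ulcers expected, a non-significant difference is not evidence of unchanged ulcer risk.

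If the sponsor prefers to keep a model, an unadjusted or Firth-penalized one, run only above a prespecified event count, would also answer the point.

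Cost: the adjusted hazard ratio is given up, and the rewording is an amendment needing IRB approval (IRB statement before the Table of Contents). No new data are required, because ulcers are already recorded (5.0) and frequencies by group are already planned (10.5.1). The endpoint keeps its name and definition.

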10.5.4 Planned Interim Analysis

Not applicable.

10.5.5 Sub-Group Analyses

Not applicable.

10.5.6 Tabulation of Individual Participant Data

Individual patient data will be listed by group.

A tabulation of patient disposition, including the number screened, the number enrolled in each schedule, the number in each patient population for analysis, the number of protocol deviations, the number that discontinued treatment and reasons for treatment discontinuation, and the number that withdrew from study and reasons for withdrawal will be presented.

APPENDIX A: Definitions for Adverse Event Reporting

A. Adverse Events (AEs)

As defined in 21 CFR 312.32:

Definition: any untoward medical occurrence associated with the use of a drug in humans, whether or not considered drug-related.

Grading: the descriptions and grading scales found in the revised NCI Common Terminology Criteria for Adverse Events (CTCAE) version 5.0 will be utilized for all toxicity reporting. A copy of the CTCAE version 5.0 can be downloaded from the CTEP website.

Attribution (relatedness), Expectedness, and Seriousness: the definitions for the terms listed that should be used are those provided by the Department of Health and Human Services' Office for Human Research Protections (OHRP). A copy of this guidance can be found on OHRP's website:

<http://www.hhs.gov/ohrp/policy/advevntguid.html>

B. Suspected Adverse Reaction (SAR)

As defined in 21 CFR 312.32:

Definition: any adverse event for which there is a reasonable possibility that the drug caused the adverse event. "Reasonable possibility" means there is evidence to suggest a causal relationship between the drug and the adverse event. "Suspected adverse reaction" implies a lesser degree of certainty about causality than adverse reaction, which means any adverse event caused by a drug.

C. Life-Threatening Adverse Event / Life Threatening Suspected Adverse Reaction

As defined in 21 CFR 312.32:

Definition: any adverse drug event or suspected adverse reaction is considered "life-threatening" if, in the view of the investigator, its occurrence places the patient at immediate risk of death. It does not include an adverse event or suspected adverse reaction that, had it occurred in a more severe form, might have caused death.

D. Serious Adverse Event (SAE) or Serious Suspected Adverse Reaction

As defined in 21 CFR 312.32:

Definition: an adverse event or suspected adverse reaction is considered "serious" if, in the view of the investigator, it results in any of the following outcomes:

- Death
- A life-threatening adverse event

- Inpatient hospitalization or prolongation of existing hospitalization
- A persistent or significant incapacity or substantial disruption of the ability to conduct normal life functions
- A congenital anomaly/birth defect
- Any other important medical event that does not fit the criteria above but, based upon appropriate medical judgment, may jeopardize the subject and may require medical or surgical intervention to prevent one of the outcomes listed above

E. Protocol Exceptions

Definition: A planned change in the conduct of the research for one participant.

F. Deviation

Definition: Any alteration or modification to the IRB-approved research without prospective IRB approval. The term “research” encompasses all IRB-approved materials and documents including the detailed protocol, IRB application, consent form, recruitment materials, questionnaires/data collection forms, and any other information relating to the research study.

A minor or administrative deviation is one that does not have the potential to negatively impact the rights, safety, or welfare of participants or others or the scientific validity of the study.

A major deviation is one that does have the potential to negatively impact the rights, safety, or welfare of participants or others or the scientific validity of the study.

APPENDIX B: Reporting Timelines

Expedited Reporting Timelines		
Event	HRPO	QASMC
Serious AND unexpected suspected adverse reaction		
Unexpected fatal or life-threatening suspected adverse reaction		
Unanticipated problem involving risk to participants or others	Report within 10 working days. If the event results in the death of a participant enrolled at WU/BJH/SLCH, report within 1 working day.	Report via email after IRB acknowledgment
Major deviation	Report within 10 working days. If the event results in the death of a participant enrolled at WU/BJH/SLCH, report within 1 working day.	
A series of minor deviations that are being reported as a continuing noncompliance	Report within 10 working days.	
Protocol exception	Approval must be obtained prior to implementing the change	
Clinically important increase in the rate of a serious suspected adverse reaction of that listed in the protocol or IB		
Complaints	If the complaint reveals an unanticipated problem involving risks to participants or others OR noncompliance, report within 10 working days. If the event results in the death of a participant enrolled at WU/BJH/SLCH, report within 1 working day. Otherwise, report at the time of continuing review.	
Breach of confidentiality	Within 10 working days.	
Incarceration	If withdrawing the participant poses a safety issue, report within 10 working days. If withdrawing the participant does not represent a safety issue and the patient will be withdrawn, report at continuing review.	

Routine Reporting Timelines		
Event	HRPO	QASMC
Adverse event or SAE that does not require expedited reporting	If they do not meet the definition of an unanticipated problem involving risks to participants or others, report summary information at the time of continuing review	Adverse events will be reported in the toxicity table in the DSM report which is typically due every 6 months.

Routine Reporting Timelines		
Event	HRPO	QASMC
Minor deviation	Report summary information at the time of continuing review.	
Complaints	If the complaint reveals an unanticipated problem involving risks to participants or others OR noncompliance, report within 10 working days. If the event results in the death of a participant enrolled at WU/BJH/SLCH, report within 1 working day. Otherwise, report at the time of continuing review.	
Incarceration	If withdrawing the participant poses a safety issue, report within 10 working days. If withdrawing the participant does not represent a safety issue and the patient will be withdrawn, report at continuing review.	

APPENDIX C: ISGPS Criteria for Delayed Gastric Emptying

DGE grade	NGT required	Unable to tolerate solid oral intake by POD	Vomiting/gastric distension	Use of prokinetics
A	4–7 days or reinsertion > POD 3	7	±	±
B	8–14 days or reinsertion > POD 7	14	+	+
C	>14 days or reinsertion > POD 14	21	+	+

DGE, Delayed gastric emptying; POD, Postoperative day, NGT, Nasogastric tube.

APPENDIX D: Modified Accordion Grading System

TABLE 5. Accordion Severity Classification of Postoperative Complications: Expanded Classification

1. Mild complication
Requires only minor invasive procedures that can be done at the bedside such as insertion of intravenous lines, urinary catheters, and nasogastric tubes, and drainage of wound infections. Physiotherapy and the following drugs are allowed-antiemetics, antipyretics, analgesics, diuretics, electrolytes, and physiotherapy.
2. Moderate complication
Requires pharmacologic treatment with drugs other than such allowed for minor complications, for instance antibiotics. Blood transfusions and total parenteral nutrition are also included.
3. Severe: invasive procedure without general anesthesia
Requires management by an endoscopic, interventional procedure or re-operation* without general anesthesia.
4. Severe: operation under general anesthesia
Requires management by an operation under general anesthesia.
5. Severe: organ system failure[†]
6. Death
Postoperative death.

*An example would be a wound reexploration under conscious sedation and/or local anesthetic.

[†]Such complications would normally be managed in an increased acuity setting but in some cases patients with complications of lower severity might also be admitted to an ICU.

ANNALS OF SURGERY

[The Accordion Severity Grading System of Surgical Complications](#)

Strasberg, Steven M.; Linehan, David C.; Hawkins, William G.
Annals of Surgery 250(2):177-186, August 2009.
doi: 10.1097/SLA.0b013e3181afde41

Accordion Severity Classification of Postoperative Complications: Expanded Classification

APPENDIX E: Expected Post-Surgical Adverse Events

Gastrointestinal:

- Delayed gastric emptying
- Pancreatic fistula
- Intraabdominal abscess
- Clostridium difficile infection
- Leak (chyle, biliary, pancreatic, gastric, enteric)
- Anastomotic ulcer
- Bowel obstruction
- Bowel perforation
- Bowel ischemia
- Mesenteric ischemia
- Colitis
- Gastritis/esophagitis

Cardiovascular:

- Myocardial infarction
- Arrhythmia
- Cardiac arrest
- Congestive heart failure
- Hemorrhage
- Deep vein thrombosis
- Pulmonary embolism
- Ischemic stroke
- Hemorrhagic stroke
- Venous or arterial thrombosis
- Hypotension

Urinary:

- Urinary retention
- Urinary tract infection
- Acute kidney injury/failure

Respiratory:

- Pneumonia
- Subcutaneous emphysema

Neurological:

- Delirium/agitation

General:

- Surgical site infection
- Pancreas endocrine insufficiency
- Pancreas exocrine insufficiency
- Bacteremia/sepsis
- Failure to thrive
- Death

APPENDIX F: Study-Specific DSM Tables

Protocol Objectives and Subject Evaluability	
Objective	# of patients evaluable for this endpoint to date
Primary	
Determine the effect of PPIs on the incidence of delayed gastric emptying within 90 days in patients after pancreaticoduodenectomy.	
Secondary	
Determine the effect of PPIs on the incidence of overall postoperative complications in the patients after pancreaticoduodenectomy.	
Determine the marginal ulcer-free survival (MUFS) within 90 days in the patients undergoing pancreaticoduodenectomy.	

Interim Analysis and Early Stopping Rules	
Does the study design include an interim toxicity analysis?	
No	
Does the study design include an interim futility analysis?	
No	
Are there early stopping rules that outline circumstances under which the study must be suspended or closed?	
No	

Response and Survival							
UPN	On tx date	# doses	Pt replaced? (y/n)	Delayed gastric emptying? (y/n)	Off tx reason	Vital status	If dead, cause

Summary of Specimen Collections			
Type of specimen	Time point	# of patients eligible for collection at this time point	% of patients who have reached this time point and had the specimen collected
N/A (no research specimens collected on this study)
